## **3. Observation Items And Monitoring Time Point**

### **1. 1. Baseline metrics**

The following data were collected during the patient screening period

Demographic data: age (yr), gender, education level, ASA grade, body mass index, diagnosis and preoperative comorbidities, and history of smoking and alcohol abuse.

Preoperative clinical data: pulse oxygen saturation (SpO2), Non-invasive blood pressure (NIBP), heart rate and other vital signs, and electrocardiogram.

The following data will be collected during the surgical treatment period:

SpO2, HR, systolic blood pressure, diastolic blood pressure, MBP, test time points including 5 minutes before induction of anesthesia, 1 minute after induction, 1 minute after laryngeal mask placement, and start of surgery. Where, data recorded 5 min before induction of anesthesia served as baseline.

The following data were collected during the PACU recovery period:

SpO2, HR, systolic BP, diastolic BP, and MBP

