### **2. Study Design And Methods**

#### **1. Research Design**

##### **1.1 Study Objectives**

The study plans to use the Chinese version of QoR-15 score to evaluate the quality of postoperative recovery after general anesthesia in elderly day surgery patients receiving remazolam or etomidate, while observing hemodynamic changes and other adverse effects.

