### **2. 3. Secondary outcome measures:**

SpO2, HR, MBP, and frequency of vasoactive medication use during anesthesia, and incidence of adverse events in the PACU. Time to the disappearance of the lash reflex after induction.

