## 2. Statistical analysis method

Data management was performed by EpiData software; SPSS26.0 software was used for statistical analysis. Quantitative variables were tested for normality by using the Shapiro - Wilk test. Comparison of quantitative variables with normal distribution between groups were performed by the t-test, and quantitative data with asymmetric distribution were analyzed by the Mann Whitney U-test. Qualitative variables were compared between groups with the chi-square test or Fisher's exact test as needed. Data for the QoR-15 score are also expressed as the median difference and their 95% confidence interval (CI). Median difference is the median of all pairwise differences between the two sets of observed values, with the 95% CI estimated by Hodges-Lehmann. Data on the frequency of adverse events were reported by the proportion difference and their 95% CI. The 95% CI of proportional differences was calculated using the Wilson program. Among other parameters, such as patient demographic parameters, SpO2, HR, MBP, and vasoactive drug application frequency, median or proportional differences and their 95% CI were calculated as described above. All analyses were assessed using two-sided tests and a P-value less than 0.05 was considered statistically significant.

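### The plan states no adjustment for the pre-induction baseline when MBP and heart rate are compared between arms: the comparison is valid, but less precise than it could be

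*Combined protocol and SAP*

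**What the plan says.** Section 1.1 (Study Objectives) sets out to evaluate recovery by QoR-15 "while observing hemodynamic changes and other adverse effects". Section 3, under Baseline metrics, lists the theatre readings of SpO2, heart rate and blood pressure: one before induction, then "1 minute after induction, 1 minute after laryngeal mask placement, and start of surgery". It assigns the pre-induction reading a role: "Where, data recorded 5 min before induction of anesthesia served as baseline".

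The secondary outcomes in sections 1.3, 3 and 4 name the measurements themselves, for example "HR, MBP, and frequency of vasoactive medication use during anesthesia". None of these lists defines a change or fall from baseline.

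The only analysis text is section 5, item 2 (Statistical analysis method). For normally distributed data: "Comparison of quantitative variables with normal distribution between groups were performed by the t-test". Otherwise: "quantitative data with asymmetric distribution were analyzed by the Mann Whitney U-test". The effect estimate is introduced for QoR-15: "Median difference is the median of all pairwise differences between the two sets of observed values". It is then extended to the haemodynamic variables: "HR, MBP, and vasoactive drug application frequency, median or proportional differences and their 95% CI were calculated as described above". No covariate, change score or repeated-measures model appears.

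**The concern.** The plan collects a baseline and labels it as such, but does not say how it enters the between-arm comparison. A later MBP reading reflects both the induction drug and where the patient started. If the starting value is left out, its variation stays in the error term, and any chance difference between the arms before induction is passed on in part to the estimated drug effect.

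This matters because the background section makes haemodynamic stability at induction part of the reason for the trial, while section 2.2 sizes the trial on QoR-15 alone. The haemodynamic comparison has no power calculation behind it. An imprecise result that shows no clear difference could be read as equal stability, so precision that costs nothing is worth having.

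**Working it through.** **Inputs.** 56 patients per arm (section 2.2); one pre-induction and three later theatre readings (section 3); two-sample tests only (section 5, item 2). The documents give neither the correlation *r* between the pre-induction and a later reading nor the SD of MBP or heart rate. I therefore take *r* from 0.3 to 0.6 as an assumption and express results in SD units. The plan states no figure on this point to reproduce; its one power statement concerns QoR-15 and does not enter here.

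**Formulas**, for a two-arm comparison with equal variance at both times:
- SE of the raw difference = SD × √(2/n). With n = 56 this is 0.189 SD, so the 95% CI half-width is 1.96 × 0.189 = 0.370 SD.
- SE(ANCOVA)/SE(raw) = √(1 − r²); the equivalent raw sample per arm is 56/(1 − r²).
- SE(change score)/SE(raw) = √(2(1 − r)).
- Dividing the two ratios, SE(ANCOVA)/SE(change score) = √((1 + r)/2).

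| r | ANCOVA/raw SE | SE cut | Equivalent n per arm | Gain in patients | ANCOVA CI half-width (SD) | Change/raw SE | ANCOVA/change SE |
|---|---|---|---|---|---|---|---|
| 0.3 | 0.954 | 5% | 61.5 | 10% | 0.353 | 1.183 | 0.806 |
| 0.4 | 0.917 | 8% | 66.7 | 19% | 0.339 | 1.095 | 0.837 |
| 0.5 | 0.866 | 13% | 74.7 | 33% | 0.321 | 1.000 | 0.866 |
| 0.6 | 0.800 | 20% | 87.5 | 56% | 0.296 | 0.894 | 0.894 |

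The last column covers the case where change scores were meant: ANCOVA would still cut the SE by 19% at r = 0.3 and by 11% at r = 0.6.

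**Carry-through of a chance imbalance.** The baseline difference between arms also has SE 0.189 SD, so about 95% of trials fall within ±0.37 SD and 29% exceed 0.2 SD in absolute size. In a raw comparison, *r* times the baseline difference passes into the estimate:
- an imbalance of 0.2 SD shifts it by 0.2 × 0.3 = 0.06 SD to 0.2 × 0.6 = 0.12 SD;
- an imbalance of 0.37 SD shifts it by 0.11 to 0.22 SD.

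**Check by simulation** (4,000 trials, 56 per arm). At r = 0.3 and 0.5 the slope of the raw estimate on the baseline difference was 0.31 and 0.49; for ANCOVA it was 0.01 and −0.01. The SE ratios were 0.95 and 0.87, as the formula predicts.

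**The case against.** Four points can be made for the plan.

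1. **It does not say that raw values are compared.** A reader might infer that they certainly are, and that the baseline enters no analysis. The documents do not go that far. A two-sample test could be run on change scores, and the word baseline together with the stated interest in changes leaves that open. The reference to observed values comes from the definition of the Hodges-Lehmann estimator, given for QoR-15 and carried over. The pre-induction reading is also one of the listed time points, so it may itself be compared between arms; an imbalance would then be seen, though not adjusted for. This stands. What remains is that no adjustment is stated, and the table shows that ANCOVA is more precise than a raw or a change-score analysis over the assumed range.

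2. **Validity is intact.** A reader might infer an inflated false-positive rate. At r = 0.5, given a baseline imbalance of 2 SE, the unadjusted test statistic is centred at 0.5 × 2 = 1 with SD 0.866 under no effect, and it rejects in about 13% of such trials. But an imbalance of 2 SE or more arises in under 5% of trials, and over all randomisations the estimate is unbiased and the error rate is 5%.

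3. **The gain depends on an unknown correlation.** It is 5% at r = 0.3 and nothing at r = 0. This stands, which is why only a range is given. Power for a difference in mmHg would need an SD and a target that the plan does not set, so I do not rely on any such figure.

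4. **Haemodynamics are secondary.** The stated purpose is recovery quality, and no haemodynamic hypothesis or margin exists. This also stands and limits the rank of the point.

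**Conclusion.** The point holds as one of precision and clarity. The plan designates a haemodynamic baseline but specifies two-sample comparisons of MBP and heart rate with no stated adjustment for it. For a correlation of 0.3 to 0.6, which is assumed, adjustment would narrow the confidence intervals by 5% to 20% relative to raw values and remove the carry-through of chance imbalance, using data already collected. These percentages do not depend on the sample size or on the SD of MBP.

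The point does not show bias, a type I error above 5%, or any effect on the QoR-15 sample size or primary conclusion. The change should be made, but the trial's main result does not turn on it.

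**What to change.** In section 5, item 2, state that MBP and heart rate at each post-induction reading will be compared between arms by ANCOVA with the pre-induction value of the same variable as covariate, reported as a baseline-adjusted mean difference with 95% CI. This replaces the t-test or Mann-Whitney choice and the Hodges-Lehmann difference for these two variables. Do not use simple change scores: their SE is 18% larger than raw at r = 0.3 and matches raw only at r = 0.5.

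A mixed model over the time points with the pre-induction value as covariate is an acceptable alternative. An average over the post-induction readings is optional; ANCOVA at each reading is enough to cure the problem.

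The cost is SAP wording and minor programming in the planned SPSS software. No extra patients, measurements or procedures are needed.

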## 2. 2. Primary outcome measures:

Quality of patient recovery at 24h after surgery (QoR-15 score)

Patients were assessed using the Chinese version of the Recovery Quality-15 (QoR-15) scale. This is a comprehensive measure of postoperative recovery, assessing the five dimensions of recovery: physical comfort (5), physical independence (2), emotional status (4), psychological support

(2), and pain (2). Each item was rated as 11 points based on its frequency in the questionnaire (higher positive items scores, lower negative items scores). The total score ranged from 0 (worst recovery quality) to 150 (best recovery quality);

order number	contents of a project	grade
1	Smooth breathing	0~10
2	Good appetite	0~10
3	Have a good rest	0~10
4	sleep quality	0~10
5	Self-care personal hygiene	0~10
6	Talk to your family and friends normally	0~10
7	Feel the medical staff medical support	0~10
8	Participate in work or daily family activities	0~10
9	Feel comfortable and can manage your emotions by yourself	0~10
10	Overall, feeling healthy	0~10
11	Moderate pain	0~10
12	acute pain	0~10
13	N and V	0~10
14	Nervous anxiety	0~10
15	Sad depression	0~10

### **2. 3. Secondary outcome measures:**

SpO2, HR, MBP, and frequency of vasoactive medication use during anesthesia, and incidence of adverse events in the PACU. Time to the disappearance of the lash reflex after induction.

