## 1. Research Background

Elderly patients have reduced organ function, often with comorbidity, and the incidence of complications and mortality are significantly higher after undergoing anesthesia and surgical trauma than those in other adult patients.[1-3] At the same time, elderly patients often have problems with hemodynamic instability such as hypotension during the induction of anesthesia.[4]

Eomidate, a widely used general anesthetic, is often used for induction of general anesthesia in elderly or hemodynamically unstable patients because of its small effects on blood pressure and heart rate. However, etomidate has an inhibitory effect on adrenal function and can cause muscle tremor and stiffness. Moreover, some studies have shown that etomidate anesthesia increases postoperative nausea and vomiting (PONV), which may not be conducive to patient prognosis and reduce satisfaction.[5]

Remazolam (RT) is a new ultra-short-acting benzodiazepine drug that has been approved for clinical use since 2019. It is characterized by rapid hydrolysis into inactive carboxylate metabolites by ubiquitous tissue esterases. Compared to the classic benzodiazepine midazolam.[6-8] Also, like the other benzodiazepines, remazolam can be antagonized by the flumazenil injection. A recent study showed that remazolam is more stable hemodynamic than propofol during anesthesia.[9]

With significant advances in surgical techniques, the proportion of patients undergoing day surgery with postoperative

complications has gradually decreased. Current perioperative care that improves the recovery of surgical patients focuses more on the time to restore normal function and the subjective postoperative experience, rather than just the incidence of complications. The Quality of Recovery (QOR) score, as an objective measure of patient-centered surgery and post-anesthesia general health, is often used to assess the quality of postoperative recovery, where QoR-15 is a reliable tool for assessing early postoperative recovery [10] and has been validated for [12] in patients undergoing various surgical procedures.

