## **Effect of general anesthesia on the quality of recovery after day surgery in elderly patients: a comparative study with etomidate induction**

### **1. Purpose Of Research**

**To compare the quality of postoperative recovery induced by general anesthesia with Remimazolam and etomidate in elderly patients undergoing day surgery.**

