##### **1.3 Primary outcome measures: quality of recovery at 24h after surgery (QoR-15 score)**

Secondary study index: time of eyelash reflex disappearance after induction; SpO2, HR, MBP, and frequency of use of vasoactive drugs during anesthesia; incidence of adverse events in PACU.

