### 2. Research methods

2.1 Study design: Randomized, controlled, parallel non-inferiority trial

Randomization: The randomization result was generated by the investigator using R software, sealed to the envelope and handed over by the patient to the anesthesia nurse before surgery, who was responsible for unpacking the randomized envelope.

Blinding: The anesthesia nurse was responsible for unpacking the randomized envelope and preparing drugs to cover the syringes (with the same appearance and volume), and blinded the anesthesiologist, postoperative visitors and patients.

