## **2. Secondary outcome measures:**

SpO2, HR, MBP, and frequency of vasoactive medication use during anesthesia, and incidence of adverse events in the PACU. Time to the disappearance of the lash reflex after induction.

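### Adverse events are a planned outcome only in the PACU, so muscle tremor or stiffness around induction, when the study drugs are given, has no scheduled record

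*Combined protocol and SAP*

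**What the plan says.** The secondary outcomes are stated three times, and each statement confines adverse events to the recovery room:

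- Section 1.3: "incidence of adverse events in PACU".
- Section 3, item 2.3: "frequency of vasoactive medication use during anesthesia, and incidence of adverse events in the PACU".
- Section 4, item 2: "incidence of adverse events in the PACU".

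For the surgical period, section 3 (Baseline metrics) schedules SpO2, HR, systolic and diastolic pressure and MBP at a pre-induction baseline and then at "1 minute after induction, 1 minute after laryngeal mask placement, and start of surgery". The only other outcomes tied to this period are vasoactive drug use and time to loss of the eyelash reflex.

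The Research Background says that "etomidate has an inhibitory effect on adrenal function and can cause muscle tremor and stiffness". Its closing paragraph makes the absence of such side effects part of the case for an alternative drug. Section 1.1 states the objective as assessing QoR-15 "while observing hemodynamic changes and other adverse effects".

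**The concern.** The randomized drugs are induction agents, but the adverse-event count begins only in the PACU. An event that starts and ends around induction, and is not a change in saturation, heart rate or blood pressure, has nowhere to be recorded. Tremor and stiffness are the clearest case, because the protocol itself names them as drawbacks of the comparator.

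At stake is the secondary safety comparison. As written, it would omit the period in which the study drugs are given, and the section 1.1 aim of watching for other adverse effects would be only partly met. An event not noted at the time may not be reliably recoverable later.

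**Working it through.** **Text check.** The plan states no figure on this point, so the first step is to ask of each relevant place whether it creates a record of tremor or stiffness around induction.

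| Place | Content | Creates that record? |
|---|---|---|
| Sections 1.3; 3 (item 2.3); 4 (item 2) | Adverse-event incidence, PACU | No: window starts too late |
| Same three places | Vasoactive drug use during anesthesia; eyelash-reflex time | No: different variables |
| Section 3, Baseline metrics | SpO2, HR and blood pressures at four time points | No: vital signs only |
| Section 1.1 | Other adverse effects, in general terms | No: no event, time or form |
| Section 5, item 1 | Safety analysis set | No: defines who is analysed, not what is collected |
| Section 5, item 2 | Proportion difference with 95% CI for adverse-event frequency | No: method only |

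The three outcome statements use a during-anesthesia window for vasoactive drugs and a PACU window for adverse events within the same list. The plan therefore distinguishes the two periods and places adverse events only in the later one.

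**What an added record could show.** Inputs: n = 56 per arm (section 2.2) and a Wilson-based interval for proportion differences (section 5, item 2). The event counts are assumptions, because the documents give none. The plan does not say how Wilson limits are combined for a difference; the Newcombe hybrid-score method is assumed, with z = 1.96.

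Wilson limits for one arm, with p = x/n:

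(l, u) = [p + z²/(2n) ± z·√(p(1−p)/n + z²/(4n²))] / (1 + z²/n)

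Difference d = p₁ − p₂ (arm 1 etomidate, arm 2 remimazolam):

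- lower = d − √[(p₁ − l₁)² + (u₂ − p₂)²]
- upper = d + √[(u₁ − p₁)² + (p₂ − l₂)²]

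Worked case, 5/56 versus 0/56:

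- p₁ = 0.0893, l₁ = 0.0387, u₁ = 0.1926
- p₂ = 0, l₂ = 0, u₂ = 3.8416/59.8416 = 0.0642
- lower = 0.0893 − √(0.0506² + 0.0642²) = 0.0893 − 0.0817 = 0.008
- upper = 0.0893 + 0.1033 = 0.193

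| Assumed events, etomidate vs remimazolam | Difference (points) | 95% CI | Half-width |
|---|---|---|---|
| 3 vs 0 | 5.4 | -2.0 to 14.6 | 8.3 |
| 4 vs 0 | 7.1 | -0.6 to 17.0 | 8.8 |
| 5 vs 0 | 8.9 | 0.8 to 19.3 | 9.2 |
| 6 vs 3 | 5.4 | -5.5 to 16.7 | 11.1 |
| 11 vs 3 | 14.3 | 1.9 to 27.0 | 12.6 |
| 17 vs 3 | 25.0 | 11.0 to 38.4 | 13.7 |

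With no events in the other arm, the interval first excludes zero at 5 events. Zero events in 56 patients would still leave a Wilson upper limit of 6.4%.

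**The case against.** The strongest reply is one of scope. Section 1 gives the purpose as "To compare the quality of postoperative recovery induced by general anesthesia with Remimazolam and etomidate", and a trial need not measure every comparator drawback named in its introduction. No hypothesis, margin or sample size depends on tremor. The documents give neither its timing nor its rate, and tremor seen in the PACU would fall inside the planned window. Section 1.1 and the safety set carry no PACU limit, so the defect could be read as a wording mismatch. The same Background sentence also names adrenal inhibition, which this point does not pursue. Finally, the Fisher test that section 5 allows is stricter than the interval: 5 versus 0 gives p = 0.057, and 6 versus 0 is needed (p = 0.027).

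Much of this stands as a limit on the point. The timing is inferred, the matter is secondary, and the counts are assumed. Adrenal inhibition is also unmeasured; it is set aside because it would need laboratory samples, whereas tremor needs only bedside observation. The Fisher result matters little for an item labelled descriptive.

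The reply does not close the gap. The unrestricted wording in section 1.1 and section 5 would permit induction events to be analysed, but nothing schedules their collection, and the three places that define the outcome exclude them.

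**Conclusion.** The concern holds. Followed as written, the adverse-event comparison leaves out induction, and no other scheduled item would capture tremor or stiffness there. That the record is missing is plain from the text. That it matters in practice rests on tremor or stiffness occurring around induction, which is inferred, so confidence in the point overall is medium.

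The number of events lost cannot be computed. Across the assumed counts, a comparison at 56 per arm would have half-widths of about 8 to 14 percentage points: informative about a large difference, not a small one. The primary QoR-15 outcome, the PACU comparison and the hemodynamic record around induction are unaffected. The change is worth making but is not critical to the trial's main conclusion.

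**What to change.** In sections 1.3, 3 (item 2.3) and 4 (item 2), redefine the outcome as the incidence of adverse events from the start of induction to PACU discharge, reported separately for the induction/intraoperative period and the PACU. Name muscle tremor/stiffness as a recorded event, present or absent, with one written definition for both arms. The anesthesiologist can record it without a new assessor, since section 2.1 says the nurse who prepares the drugs "blinded the anesthesiologist, postoperative visitors and patients". Analyse it in the safety set with the proportion difference and Wilson-based 95% CI already planned, and label it descriptive.

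The cost is a few form fields and one definition, with no new visit, procedure or sample. The drawback is one more secondary comparison in a plan that has no multiplicity rule, which is why it should be read descriptively.

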## **4. Efficacy Evaluation Criteria**

### **1. Main outcome measures:**

The primary outcome measure was the quality of recovery at 24h after surgery (QoR-15 score), recording the QoR-15 score 1 day before surgery, 1 day after surgery (POD 1) and 2 days after surgery (POD 2). The POD 1 score was the primary study outcome.

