## 2.2 Sample size estimation:

The primary outcome measure was the quality of postoperative patient recovery (QoR-15 score). According to previous studies, the minimal clinically important difference was 8. The non-inferiority bound for the mean difference between groups was set to -8. Referring to previous studies, the standard deviation (SD) of the QoR-15 scale is 14, and accounting for a 10% shedding rate, 112 achieves 90% of efficacy with a type 1 error of 0.05. We chose to include 112 subjects in this study for the analysis, with 56 subjects in each group.

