## **5. Statistical treatment**

### 1. Analyze the crowd

- 1) Full analysis set (FAS): Subject set following the principle of intentional treatment (Intention To Treat, ITT): the data set consisting of all subjects participating in treatment and with baseline efficacy evaluation.
- 2) Compliance with the protocol set (PPS): refers to the completed trial and excluded the treatment population group with serious protocol violations (refers to which the study subjects violated the inclusion criteria or exclusion criteria).
- 3) Safety analysis set (SS): means the set of all subjects enrolled, with a study intervention, and with at least one baseline level safety evaluation.
- 4) Efficacy analysis will be conducted on the basis of the full analysis set and the compliant protocol set. All baseline demographic data analyses will be conducted based on the full

analysis set, and safety evaluations will be conducted on the safety set.

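### Pre-operative QoR-15 is collected but left out of the POD 1 comparison; adjusting for it is an optional, low-cost gain in precision for the mean difference judged against -8

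*Combined protocol and SAP*

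**What the plan says.** Section 4 (Efficacy Evaluation Criteria, Main outcome measures) schedules three assessments: "recording the QoR-15 score 1 day before surgery, 1 day after surgery (POD 1) and 2 days after surgery (POD 2"). It then fixes the endpoint: "The POD 1 score was the primary study outcome". The endpoint is the POD 1 score itself, not a change from the pre-operative value.

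Section 2.2 (Sample size estimation) puts the margin on the mean scale: "The non-inferiority bound for the mean difference between groups was set to -8".

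Section 5 (Statistical treatment, Statistical analysis method) gives these between-group methods for quantitative data:
- If normal: "Comparison of quantitative variables with normal distribution between groups were performed by the t-test".
- If not normal: the Mann-Whitney test.
- For QoR-15 in addition: "Data for the QoR-15 score are also expressed as the median difference and their 95% confidence interval (CI"), by the Hodges-Lehmann method.

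No section describes ANCOVA, regression or a change score. The statistical section mentions a baseline efficacy value only under Analyze the crowd, as a condition for entering the full analysis set (FAS). For the analysis sets it says: "Efficacy analysis will be conducted on the basis of the full analysis set and the compliant protocol set".

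**The concern.** Non-inferiority will turn on where the lower confidence limit falls relative to -8. The plan already pays for a pre-operative measurement on the same 15-item scale in the same patient, then leaves it out of the comparison. If that score predicts the POD 1 score, part of the between-patient variation could be removed and the interval for the mean difference narrowed without recruiting anyone. What is at stake is precision and power. Bias and type I error are not in question.

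**Working it through.** **Inputs.** Margin 8, SD 14 ("the standard deviation (SD) of the QoR-15 scale is 14"), 56 per arm and 10% dropout, all from section 2.2. That leaves 56 × 0.9 = 50.4, taken as 50 per arm (N = 100). The true difference is set to 0. Section 2.2 does not say whether its 0.05 is one-sided or two-sided; section 5 uses two-sided tests and 95% intervals. Both readings are shown. The correlation r between pre-operative and POD 1 scores is not in the documents, so a range of 0 to 0.5 is assumed.

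**Step 1: the plan's own figure.** By the normal approximation at one-sided 0.05, power is 91.6% at 56 per arm and 88.7% at 50 per arm. This brackets the stated 90%. At one-sided 0.025 (a two-sided 95% interval) the figures are 85.6% and 81.5%. The steps below use the t distribution, which gives slightly lower values.

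**Step 2: unadjusted mean difference.**
- SE = 14 × √(2/50) = 2.80.
- 95% half-width = t(0.975; 98) × 2.80 = 1.9845 × 2.80 = 5.56.
- Power (noncentral t, noncentrality 8/2.80 = 2.857) = 80.8%, or 88.3% at one-sided 0.05.
- With this half-width, the observed difference must lie above -8 + 5.56 = -2.44 to pass.

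**Step 3: ANCOVA with the slope estimated.** SE = 14 × √(1 − r²) × √[(2/50)(1 + 1/96)], with 97 degrees of freedom. The factor 1 + 1/96 is the expected cost of estimating the slope. For r = 0.3, SE = 2.685 and the half-width is 1.9847 × 2.685 = 5.33.

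| Analysis | 95% half-width | Observed difference must exceed | Power, two-sided 95% CI | Power, one-sided 0.05 |
|---|---|---|---|---|
| Unadjusted | 5.56 | -2.44 | 80.8% | 88.3% |
| ANCOVA, r=0 | 5.59 | -2.41 | 80.3% | 88.1% |
| ANCOVA, r=0.1 | 5.56 | -2.44 | 80.7% | 88.3% |
| ANCOVA, r=0.2 | 5.47 | -2.53 | 81.9% | 89.2% |
| ANCOVA, r=0.3 | 5.33 | -2.67 | 83.9% | 90.6% |
| ANCOVA, r=0.4 | 5.12 | -2.88 | 86.7% | 92.4% |
| ANCOVA, r=0.5 | 4.84 | -3.16 | 90.1% | 94.7% |

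**Step 4: break-even.** Setting (1 − r²)(97/96) = 1 gives r = 1/√97 = 0.10. This is where the expected gain is zero, not where it becomes useful. In simulated normal trials at N = 100, the adjusted interval was the narrower one in about 20% of trials at r=0, 39% at 0.1, 73% at 0.2, 94% at 0.3 and 100% at 0.5.

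**Step 5: in patients.** Effective size per arm is 50/[(1 − r²)(1 + 1/96)]. The gain equals about 3 extra patients in total at r=0.2, 9 at 0.3 and 32 at 0.5.

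**Step 6: against the Hodges-Lehmann interval.** With simulated left-skewed scores of SD 14 (reflected gamma, an assumption), mean half-widths were:

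| Skew (gamma shape) | Hodges-Lehmann | ANCOVA, r=0.3 | ANCOVA, r=0.5 |
|---|---|---|---|
| Strong (1.5) | 4.3 | 5.3 | 4.9 |
| Moderate (4) | 5.2 | 5.3 | 4.8 |
| Slight (16) | 5.6 | 5.3 | 4.8 |

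ANCOVA type I error at a true difference of -8 was 0.024 to 0.027 in the skewed simulations, close to the nominal 0.025.

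**The case against.** **This is a preference, not a defect.** Nothing in the plan promises baseline adjustment, and an unadjusted comparison of POD 1 scores answers the stated question. That stands. A reader might infer that the planned analysis is biased or invalid; the documents do not support this, because allocation is randomised.

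**The benefit depends on a number nobody has given.** This is true. At r of 0.1 to 0.2 the gain is negligible, and only at 0.4 to 0.5 is it useful. A reader might infer that adjustment would bring power back to the planned 90%. On the two-sided reading that needs r near 0.5, which no passage shows. On the one-sided reading power is already 88.3%, so there is less to recover. What survives is the asymmetry: the loss at r=0 is very small.

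**The comparator is not the interval the SAP names.** For QoR-15 the SAP names only the Hodges-Lehmann interval, and the scale is bounded ("The total score ranged from 0 (worst recovery quality) to 150 (best recovery quality"), so skew is possible. Under strong skew that interval can be narrower than ANCOVA even at r=0.5. This also stands, so it cannot be said that adjustment narrows whatever interval the trial would report. But the Hodges-Lehmann interval does not estimate the mean difference on which -8 is set, so its width does not answer the same question.

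**Missing baselines.** A reader might think the change needs an imputation rule. FAS entry already requires a baseline efficacy evaluation. If that means the pre-operative QoR-15, the natural reading, no FAS patient lacks the covariate and imputation there is moot.

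**Conclusion.** The point holds as an optional improvement in precision. The pre-operative score is collected and enters no POD 1 comparison; its only possible use in the statistical section is as a condition of FAS entry. Relative to the unadjusted mean-difference interval, adjustment narrows the 95% half-width by about 4% at r=0.3 and 13% at r=0.5. Two-sided power rises by about 3 and 9 percentage points, or by about 2 and 6 points if one-sided 0.05 was meant. If r=0 the cost is about 0.03 points of half-width and under 0.5 percentage points of power.

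These figures rest on 50 evaluable patients per arm, SD 14, a true difference of 0, approximately normal scores and an assumed r.

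**What to change.** Pre-specify as the primary analysis an ANCOVA of POD 1 QoR-15 on treatment, with pre-operative QoR-15 as covariate, in both the FAS and the per-protocol set. Judge non-inferiority by comparing the lower confidence limit of the adjusted mean difference with -8, and state the confidence level. Keep the unadjusted mean difference and the Hodges-Lehmann interval as sensitivity analyses, so that adjusted and unadjusted results cannot be chosen between after the data are seen.

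State that the baseline evaluation required for FAS entry is the pre-operative QoR-15. No separate imputation rule is then needed in the FAS; if the FAS definition is changed, the handling of a missing pre-operative score must be written to match.

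The cost is a few lines of SAP text and one model in SPSS, which the plan already uses. No new data or visits are needed.
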